9. STATISTICAL CONSIDERATIONS

9.1. Statistical Hypotheses

The null and alternative hypotheses for analysis of the primary estimand variable are:

 H_0 : $u_{JZP385} = u_{Placebo}$

 H_1 : $u_{JZP385} \neq u_{Placebo}$

Specifically, the null hypothesis states that there is no difference in the mean change on the TETRAS composite outcome score from Baseline to Week 12 between each dose of JZP385 and the placebo control group. The alternative hypothesis is that the mean change on the TETRAS composite outcome score from Baseline to Week 12 is not equal between each dose of JZP385 and the placebo control group.

The null and alternative hypotheses for analysis of the key secondary estimand variable are:

 H_0 : $p_{JZP385} = p_{Placebo}$

 H_1 : p JZP385 \neq p Placebo

Specifically, the null hypothesis states that there is no difference in the proportion of participants who improved by ≥ 1 point on the CGI-S from Baseline to Week 12 between each dose of JZP385 and the placebo control group. The alternative hypothesis is that the proportion of participants who improved by ≥ 1 point on the CGI-S from Baseline to Week 12 is not equal between each dose of JZP385 and the placebo control group.

Each JZP385 treatment group will be compared individually to placebo. The remaining secondary and exploratory endpoints will not be controlled within the formal hypothesis test for type I error. All safety analyses will be descriptive; no formal statistical testing will be performed.

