9.4.2. Primary Estimand

The primary estimand is a composite outcome score of the sum of modified items 1 to 11 of the TETRAS-ADL and modified items 6 and 7 of the TETRAS-PS. For the primary estimand, the scoring of each of the items 1 to 11 of the TETRAS-ADL subscale as well as items 6 and 7 of the TETRAS-PS will be modified. For TETRAS-ADL, each item will be modified from 5 response items to 4 response items by collapsing options 0 and 1 together and for TETRAS-PS, each item will be modified from 9 response items (due to 0.5 scoring increments) to 4 response items. Each item has a maximum score of 3. As item 6 of the TETRAS-PS includes assessments for both hands, there are a total of 3 items from the TETRAS-PS and 11 items from the TETRAS-ADL that contribute to a 14-item TETRAS composite outcome score. The total range of the TETRAS composite outcome score that will be used for the primary analysis will therefore be 0 to 42.

The attributes of the primary estimand are listed below:

- Treatment: 10, 20, and 30 mg/day JZP385 and placebo.
- Population: Adults with moderate to severe ET.
- Variable: Change from Baseline to Week 12 on the TETRAS composite outcome score.
- Intercurrent Events:
 - Discontinuation of study intervention due to an AE, for lack of efficacy, or any other reason. Participants who experience this type of intercurrent event will be addressed by hypothetical strategy.
 - Any change to concomitant antitremor medication use after the initiation of study intervention (refer to Section 9.4.1.2). Participants who experience this type of intercurrent event will be addressed by treatment policy.
- Summary: Difference in the mean TETRAS composite outcome score from Baseline to Week 12 between each dose of JZP385 and placebo.

For the main estimator analysis, a MMRM will be used to include the difference in the TETRAS composite outcome score from the Baseline Visit to Weeks 4, 8, and 12. The model will include fixed effects for treatment group, week, treatment group by week interaction, baseline TETRAS composite outcome score stratification (≤ 17 or > 17), baseline concomitant antitremor medication stratification (Yes or No), baseline TETRAS composite outcome score by week interaction, baseline TETRAS composite outcome score as a continuous covariate, and week repeated within each participant as a repeated effect. An unstructured variance-covariance matrix will be used to model the correlation among repeated measurements.

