9.4.3.2. Secondary Endpoints

For the analysis of CGI-C and PGI-C at Week 12, the CMH test stratified by the randomization stratum will be used for the comparison between each dose of JZP385 and placebo.

For the analysis of change from Baseline to Week 12 on the TETRAS-ADL, TETRAS-PS, TETRAS-PS upper limb score (item 4), and TETRAS total score, the same MMRM models used for the primary estimand will be used.

For the analysis of change of QUEST score from Baseline to Week 12, an analysis of covariance (ANCOVA) model will be used. The model will include treatment group, randomization stratum, and corresponding baseline value as fixed effects.

For the analysis of change of ETEA score from Baseline to Week 12, an ANCOVA model will be used. The model will include treatment group, randomization stratum, and corresponding baseline value as fixed effects.

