7.6. Changes to Planned Analyses

Section 9.4.1.4 of the Protocol outlines the approach to imputation of missing item scores, as part of the TETRAS composite outcome score. Based on these rules, it was possible for a participant to have a missing TETRAS PS score at a visit and still have a valid composite outcome score. The rules have been amended to change the imputation of missing item scores to be managed within the individual subscale scores (ADL or PS) before the composite outcome score is calculated. The details of the new calculation are specified in Section 7.2.5.

The mITT Analysis Set defined in the Protocol Section 9.3 has been updated to ITT, to include all randomized participants for the primary efficacy analyses.

For Adverse Events of Special Interests defined in Protocol Section 8.4.6, presyncope was removed in the formal definition of AEOSI in Section 10.2.1.

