9.1.2. Primary Analyses

For the main analysis of the primary efficacy endpoint, a MMRM will be used to include the change in the TETRAS composite outcome score from Baseline to Weeks 4, 8, and 12.

$$dTCOM_{ij} = \alpha_i + \beta_1 * baseTCOM_i + \beta_2 * week_j + \beta_3 * treatment_i + \beta_4 * treatment_i * week_j + \beta_5 * baseTCOM_i * week_i + \beta_6 * stratum_i + \varepsilon_{ij}$$

The model will include treatment group ($treatment_i$), baseline TETRAS composite outcome score ($baseTCOM_i$), week (as a discrete factor, $week_j$), treatment group by week interaction ($treatment_k * week_j$), week by baseline interaction ($week_j * baseTCOM_i$), and randomization

stratum ($stratum_i$) as fixed effects, and week repeated within each participant as a repeated effect (α_i). For the purposes of this model, "week" refers to the treatment visit, as determined using the windows specified in Section 7.2.3. An unstructured variance-covariance matrix will be used to model the correlation among repeated measurements. If the model fails to converge on the Newton-Raphson Algorithm, the alternative Fisher scoring algorithm should be explored before considering other variance-covariance structures. Kenward-Roger's degrees of freedom will be used.

Least squares mean and standard error for Week 12 will be provided for each treatment group. The difference between the LS means of JZP385 and placebo for Week 12, along with the SE of the difference, 95% CI and associated p-value corresponding to testing the hypothesis of no difference between the treatment groups will also be provided.

The assumption of normality will be examined by obtaining a histogram and a QQ-plot on studentized residuals. Based on these plots, if there exists evidence to suggest the departure from the normality assumption, a non-parametric MMRM with the covariate and response variables replaced by their ranks will be used for the primary analysis.

The following is an example of SAS code for linear mixed model analysis:

PROC MIXED;

CLASS PATIENT TRT WEEK STRATUM;

MODEL CHG = BASELINE TRT WEEK STRATUM TRT*WEEK BASELINE*WEEK /

RESIDUAL OUTP=RESIDUAL DDFM=KR;

REPEATED WEEK/TYPE=UN SUB=PATIENT;

LSMEANS TRT*WEEK / CL DIFF ALPHA=0.05;

RUN;

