will be analyzed similarly with MMRM. The MMRM will include the difference from Baseline to Weeks 4, 8, and 12. The model will include treatment group, corresponding baseline, week (as a discrete factor), treatment group by week interaction, and randomization stratum as fixed effects, and participant as a random effect. If the model fails to converge on the Newton-Raphson Algorithm, the alternative Fisher scoring algorithm should be explored before considering other variance-covariance structures. The first alternative variance-covariance matrix will be autoregressive. Kenward-Roger's degrees of freedom will be used.

LS mean and SE for Week 12 will be provided for each treatment group. The difference between the LS means of JZP385 and placebo for Week 12, along with the SE of the difference, 95% CI and associated p-value corresponding to the testing hypothesis of no difference between the treatment groups will also be provided.

The assumption of normality will be examined by obtaining a histogram and a QQ-plot on studentized residuals. Based on these plots, if there is evidence to suggest the departure from the normality assumption, a non-parametric MMRM with the covariate and response variables replaced by their ranks will be used.

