9.3. Exploratory Endpoints

9.3.1. Analysis of Exploratory Efficacy Continuous Endpoints

The continuous exploratory endpoints include the change from Baseline to Weeks 4 and 8 on:

- The TETRAS composite outcome score
- TETRAS-ADL
- TETRAS-PS
- TETRAS upper limb score (item 4)
- TETRAS total score

The analyses results will be derived from the MMRM models for the Week 12 analysis used in the primary estimand (Section 9.1.2), key secondary estimand (Section 9.2.2), and secondary endpoints (Section 9.2.3).

For the analyses of exploratory endpoints:

- The change from baseline to Week 12 on the modified items 6 and 7 of the TETRAS-PS (where each item is modified from 9 response items to 4 response items as specified in Section 9.1.1).
- The change from baseline to Week 12 on the sum of modified items 1 to 11 of the TETRAS-ADL subscale (where each item is modified from 5 response items to 4 response items by collapsing options 0 and 1 together).

MMRM models similar to the one used in analysis for primary estimand (Section 9.1.2) will be used.

For the analysis of change in SF-36v2 score from Baseline to Week 12, a descriptive summary at each scheduled visit along with change from Baseline to Week 12 will be summarized and listed.

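### SAP 9.2.6.2 specifies a different model from the primary MMRM that the protocol requires for four TETRAS secondary endpoints, and SAP 7.6 does not declare the change

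*SAP*

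**What the plan says.** Protocol 9.4.3.2 covers change to Week 12 on TETRAS-ADL, TETRAS-PS, TETRAS-PS item 4 and the TETRAS total score. For all four it says that "the same MMRM models used for the primary estimand will be used". The primary model in Protocol 9.4.2 has baseline-by-week and week as a repeated effect, and adds: "An unstructured variance-covariance matrix will be used to model the correlation among repeated measurements". The example code in SAP 9.1.2 matches it: "REPEATED WEEK/TYPE=UN SUB=PATIENT", with no RANDOM statement.

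SAP 9.2.6.2 says the four endpoints are analysed similarly with an MMRM. It then lists treatment, corresponding baseline, week, "treatment group by week interaction, and randomization stratum as fixed effects, and participant as a random effect". There is no baseline-by-week term, no starting covariance and no code. The only structure named is a fallback: "The first alternative variance-covariance matrix will be autoregressive".

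SAP 7.6 declares three departures from the protocol. These are the item-level imputation rule, the analysis set ("The mITT Analysis Set defined in the Protocol Section 9.3 has been updated to ITT") and the removal of presyncope from the adverse events of special interest. The model for these endpoints is not among them.

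SAP 9.3.1 takes the Week 4 and 8 results for the same scores from the models for the primary, key secondary "and secondary endpoints (Section 9.2.3"). Section 9.2.3 is the CGI-S sensitivity analysis, not these models.

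**The concern.** Two competent programmers could fit different models to four of the eight secondary efficacy endpoints. One would carry over the unstructured repeated-measures model. The other would follow the listed terms and fit a participant random intercept with a single residual variance. The second model forces the same variance at Weeks 4, 8 and 12, and a plain autoregressive fallback does the same.

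If the true variance changes over visits, the Week 12 comparison gets a standard error built from the average variance instead of the Week 12 variance. With rising variability, the Week 12 intervals are too narrow and the Week 4 intervals too wide; with falling variability the reverse holds. The exploratory Week 4 and 8 results come from the same models, so they are affected too.

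Closely related scores could also be treated differently. Under SAP 9.3.1 the sum of modified ADL items 1 to 11 uses a model like that of 9.1.2, while the full TETRAS-ADL follows 9.2.6.2.

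**Working it through.** **The plan's own figure.** The documents give no SE or power for these four endpoints. The nearest figure is for the composite (Protocol 9.2, SAP 5.3): 80 per arm, difference 3.1, SD 6.0, two-sided 0.05, power 90%. The SE is 6.0 × √(2/80) = 0.949, and the noncentral t gives 90.1%. The figure reproduces and is not disputed.

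**Inputs.** SAP 5.3 gives SDs of change at Day 28 in the earlier study of 5.86 and 5.47, mean (5.86 + 5.47)/2 ≈ 5.67. The assumed Week 12 SD is 6.0. Interpolating gives about 5.83 at Week 8. SAP 5.3 itself expects a small increase in variability. The other SD sets below are assumptions.

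**Closed form, complete data, n per arm.**
- Correct Week 12 SE of a difference: SD₁₂ × √(2/n).
- SE from a random intercept with one residual variance: √(mean of the three visit variances) × √(2/n).
- Ratio r = √(mean variance)/SD₁₂, which does not depend on n.
- Actual level of a nominal 5% test: 2 × P(Z > 1.96 r).

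For the plan's figures: mean variance = (5.67² + 5.83² + 6.0²)/3 = (32.15 + 33.99 + 36.00)/3 = 34.05, and √34.05 = 5.84. Then r = 5.84/6.0 = 0.97, the level is 5.7% and the coverage of a 95% interval is 94.3%.

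**Simulation.** No treatment effect, 4 arms of 100, visit correlations 0.65 to 0.75, about 20% dropout missing at random, REML, 2,000 trials per SD set (3,800 for the first). The SE ratio is the mean Week 12 SE of the random-intercept model relative to unstructured with baseline-by-week.

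| SDs at Weeks 4/8/12 | Mean variance | r | Level, closed form | Simulated SE ratio | Simulated rejection, random intercept vs unstructured |
|---|---|---|---|---|---|
| 5.67/5.83/6.0 (plan, composite) | 34.05 | 0.97 | 5.7% | 0.97 | 6.0% vs 5.3% |
| 5/5.5/6 (assumed) | 30.42 | 0.92 | 7.2% | 0.91 | 7.4% vs 5.4% |
| 4.5/5.5/6.5 (assumed) | 30.92 | 0.86 | 9.4% | 0.84 | 10.7% vs 5.0% |
| 6/5.5/5 (assumed fall) | 30.42 | 1.10 | 3.1% | 1.11 | 2.5% vs 5.1% |

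The Monte Carlo SE of the rejection rates is about 0.4 to 0.7 points.

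**Other structures, same simulation.**
- Plain autoregressive is no better than the random intercept: SE ratios 0.98, 0.92, 0.85 and 1.12.
- Heterogeneous compound symmetry gave 0.998 in each of the last three sets.
- Heterogeneous autoregressive gave 0.994 in the first, third and fourth sets (500 trials each).
- Adding baseline-by-week to the random-intercept model moved the mean SE by under 0.1%, with or without a true interaction.

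**Second, smaller simulation** (300 runs per set, about 20% dropout). Mean SE, random intercept over unstructured:
- 6/6/6: 0.922/0.926 = 1.00.
- 5/5.5/6: 0.838/0.919 = 0.91.
- 4/5/6: 0.762/0.917 = 0.83.
- 7/6.5/6: 1.015/0.929 = 1.09.

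Rejection, random intercept vs unstructured, was 4.0% vs 4.7%, 7.7% vs 5.3%, 11.7% vs 5.7% and 5.3% vs 6.7%, with Monte Carlo error of about 1.3 points. With equal variances the problem disappears, as it should. At this number of runs the falling-variance case shows the larger SE but does not settle the rejection rate.

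**The case against.** The best defence is that SAP 9.2.6.2 means the primary model and is loosely worded. It says the analysis is similar, treats week as discrete and repeats the 9.1.2 convergence sentence. It also speaks of a first alternative matrix, which presupposes a starting one, and the only one the SAP names is unstructured. SAP 9.1.2 is loose too: its equation has a participant-indexed term, yet its code has only a REPEATED statement. Silence in 7.6 fits no intended change. Moreover, 9.2.6.2 never states a single residual variance or rules out a heterogeneous autoregressive form.

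That reading is possible and may be what was intended; under it the standard-error problem disappears. It does not cure the text. The listed terms differ from 9.1.2, and a single residual variance and equal-variance autoregression are the ordinary meanings of the words used. The protocol also keeps the two descriptions apart: a repeated effect for the primary MMRM (9.4.2) and a participant random effect for the time-course mixed model (9.4.4). Even on the generous reading, baseline-by-week is missing without being declared.

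Four further points stand as limits:
- On the plan's own SDs the effect is about 3% of the SE, and the simulated 6.0% against 5.3% is close to Monte Carlo noise. The larger figures rest on assumed SD changes.
- Protocol 9.1 says: "The remaining secondary and exploratory endpoints will not be controlled within the formal hypothesis test for type I error". The primary and key secondary tests are untouched.
- A fallback will rarely be needed with three visits and about 400 participants.
- The wrong reference in 9.3.1 is clerical. It is not evidence of a different model; it only fails to settle which one is meant.

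**Conclusion.** The concern holds. SAP 9.2.6.2 conflicts with Protocol 9.4.3.2 on the baseline-by-week term and the participant random effect, leaves the starting covariance unstated, and the change is not declared in SAP 7.6.

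The numerical consequence is conditional on the literal reading and on variance differing by visit. At Week 12 it runs from an SE about 3% low (level about 6%) on the plan's composite figures, to 9% and 16% low (about 7% and 9% to 11%) under the assumed rises, to about 11% high (about 3%) under the assumed fall. This is a range and not a prediction: the documents give no visit-wise SDs for the four scores, and the 5.67 and 6.0 describe the composite, one observed in the earlier study and one assumed for this trial. The missing baseline-by-week term is a mismatch with almost no effect on the SE.

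The harm is confined to intervals and nominal p-values of supportive endpoints. It should be corrected, but no confirmatory conclusion depends on it.

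**What to change.** Replace the model sentence in SAP 9.2.6.2 with a reference: the model in Section 9.1.2 with the corresponding baseline score. That means unstructured within-participant covariance through REPEATED, baseline-by-week included and no participant random effect.

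Keep a pre-specified fallback order here, because 9.1.2 names none. After Fisher scoring, use structures with visit-specific variances, for example heterogeneous autoregressive and then heterogeneous compound symmetry, in place of plain autoregressive. In SAP 9.3.1, change the secondary-endpoint reference from 9.2.3 to 9.2.6.2.

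If the random-effect model is really intended, declare it in 7.6 with a reason.

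The cost is one model sentence, one fallback sentence and one cross-reference. The primary-analysis code is reused. Unstructured covariance over three visits needs 3 × 4/2 = 6 parameters against 2 for the random intercept, which is small for about 400 participants.

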9.2.6.3. Change from Baseline to Week 12 of QUEST score

The Quality of Life in Essential Tremor Questionnaire (QUEST) was developed to specifically assess the impact of ET on health-related quality of life (Tröster 2005). The QUEST is a 30-item questionnaire comprising 5 subscales (physical, psychosocial, communication, hobbies/leisure, and work/finance), besides participants also provided assessments on overall health status, overall quality of life, tremor self assessment plus 4 additional items under general information relating to sexual function, satisfaction with tremor control, medication side effects and work status.

For the analysis of change of QUEST score from Baseline to Week 12, an analysis of covariance (ANCOVA) model will be used for related items on a continuous scale. The model will include treatment group, randomization stratum, and corresponding baseline value as covariates. For items on categorical scale, shift tables will be provided to detect change from Baseline to Week 12. No participant level imputation will be conducted to missing data or data after intercurrent events.

9.2.6.4. Change from Baseline to Week 12 of ETEA score

The Essential Tremor Embarrassment Assessment (ETEA) is a patient-rated questionnaire administered by a health care provider or researcher that contains 14-items assessing embarrassment related to tremor. Participants provide a simple response (disagree or agree) to each of the 14-items, the sum of which yields an initial score (Score A, range = 0 to 14). Participants then provide a more nuanced response to each question on a 0 to 5 point Likert scale ranging from disagree (0) to agree strongly (5). The sum of the nuanced responses yields a second score (Score B, range = 0 to 70). Higher scores on both the simple and nuanced responses indicate greater embarrassment.

For the analysis of change of ETEA score from Baseline to Week 12, an ANCOVA model will be performed using the PROC MIXED SAS procedure. The model will include treatment group, randomization stratum, and corresponding baseline value as covariates. No participant level imputation will be conducted to missing data or data after intercurrent events.

9.3. Exploratory Endpoints

9.3.1. Analysis of Exploratory Efficacy Continuous Endpoints

The continuous exploratory endpoints include the change from Baseline to Weeks 4 and 8 on:

- The TETRAS composite outcome score
- TETRAS-ADL
- TETRAS-PS
- TETRAS upper limb score (item 4)
- TETRAS total score

The analyses results will be derived from the MMRM models for the Week 12 analysis used in the primary estimand (Section 9.1.2), key secondary estimand (Section 9.2.2), and secondary endpoints (Section 9.2.3).

For the analyses of exploratory endpoints:

- The change from baseline to Week 12 on the modified items 6 and 7 of the TETRAS-PS (where each item is modified from 9 response items to 4 response items as specified in Section 9.1.1).
- The change from baseline to Week 12 on the sum of modified items 1 to 11 of the TETRAS-ADL subscale (where each item is modified from 5 response items to 4 response items by collapsing options 0 and 1 together).

MMRM models similar to the one used in analysis for primary estimand (Section 9.1.2) will be used.

For the analysis of change in SF-36v2 score from Baseline to Week 12, a descriptive summary at each scheduled visit along with change from Baseline to Week 12 will be summarized and listed.

9.3.2. Analysis of Exploratory Dichotomous Endpoints

For the analyses of proportion of participants reported as much improved on the PGI-C and CGI-C at Weeks 4 and 8, as well as proportion of participants improved (≥ 1 point decrease) from Baseline to Weeks 4 and 8, the similar analysis to Section 9.2.2 will be conducted. Week 4 and Week 8 data will be analyzed separately. CMH test stratified by the randomization stratum will be used for the comparison between each dose of JZP385 and placebo. Study dropouts and missing observations will be handled by multiple imputation (MI) as stated in Section 9.2.2. No sensitivity analyses or supplemental analysis are planned.

